Premenopausal patients in this study will be administered goserelin in addition to ribociclib and letrozole. Estrogen deprivation therapy is the core treatment modality in patients with ER+ advanced breast cancer. Endocrine therapy options for premenopausal women with ER+ advanced breast cancer (locally advanced, recurrent, or metastatic breast cancer) include selective ER modulators (SERM; e.g. tamoxifen, raloxifene), and luteinizing hormone-releasing hormone agonists (LHRHa; e.g. goserelin). Blocking estrogen signaling with tamoxifen has been the main approach in treatment for premenopausal women with ER+ breast cancer for over 35 years. Current guidelines also recommend treating premenopausal women with advanced HR+ breast cancer with an ovarian function suppression treatment and following treatment recommendations for post-menopausal women, such as non-steroidal AIs (NCCN breast cancer guidelines version 3.2014).

Ovarian suppression of estrogen release with LHRH agonists such as goserelin is effective in preventing relapse in premenopausal women with early stage ER+ breast cancer (Klijn 2001).

3 Objectives and endpoints

Objectives and related endpoints are described in [Table 3-1](#) below.

Table 3-1 Objectives and related endpoints

Objective	Endpoint	Analysis
Primary		Refer to Section 10.4

• The primary objective of this study is the assessment of the clinical benefit rate for the total population and for cohorts A and B separately:

- To assess the clinical benefit rate (CBR) after 24 weeks for ribociclib (LEE011) in combination with letrozole among postmenopausal women and men with hormone receptor positive, HER2- negative, advanced breast cancer who received no prior treatment for advanced disease. (70% group)
- To assess the clinical benefit rate (CBR) after 24 weeks for ribociclib (LEE011) in combination with letrozole and goserelin among pre-, and perimenopausal women who received no prior treatment for advanced disease as well as pre-, peri- and postmenopausal women and men with hormone receptor positive, HER2- negative, advanced breast cancer who received no more than 1 prior chemotherapy and 2 prior lines of endocrine therapy for advanced disease (30% group)

Clinical Benefit Rate (CBR) after 24 weeks of treatment as defined by RECIST 1.1 as percentage of patients with CR, PR or SD lasting 24 weeks or longer as well as patients with NCRNPD >24 for patients with non-measurable disease

Objective	Endpoint	Analysis

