10.4.1 Variable

The **Clinical Benefit Rate (CBR)** is the proportion of patients with a best overall response of confirmed complete (CR) or partial (PR) response or stable disease (SD) or non-complete response, non-progressive disease (NCRNPD) by Week 24. The best overall response for each patient is determined from the sequence of investigator overall lesion responses according to RECIST 1.1. To be assigned a best overall response of CR at least two determinations of CR at least 4 weeks apart before progression are required. To be assigned a best overall response of PR at least two determinations of PR or better at least 4 weeks apart before progression (and not qualifying for a CR) are required. To be assigned a stable disease, two determinations of SD at least 12 weeks apart (and not qualifying for PR or PD) are required.

For further details, please refer to Appendix 14-2: Guidelines for Response, Duration of Overall Response, TTF, TTP, Progression-Free Survival and Overall Survival (based on RECIST 1.1).

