1.2 Study objectives and endpoints

Objectives and related endpoints are described in the table below (in accordance with Table 3-1 from the protocol).

Primary Objective	Endpoint

The primary objective of this study is the assessment of the clinical benefit rate after 24 weeks for the total population and for cohorts A and B separately:
 
1. Cohort A: postmenopausal women and men who received no prior treatment for advanced disease. (70% group)2. Cohort B: pre-, and perimenopausal women who received no prior treatment for advanced disease as well as pre-, peri- and postmenopausal women and men who received no more than 1 prior chemotherapy and 2 prior lines of endocrine therapy for advanced disease (30% group)	Clinical Benefit Rate (CBR) after 24 weeks of treatment as defined by RECIST 1.1 as percentage of patients with CR, PR or SD until week 24 or longer as well as patients with NCRNPD >24 weeks for patients with non-measurable disease

Secondary Objectives	Endpoint

To assess the clinical benefit rate (CBR) after 24 weeks among Cohort B1 and B2:
	
Clinical Benefit Rate (CBR) after 24 weeks of treatment as defined by RECIST 1.1 as percentage of patients with CR, PR or SD until week 24 or longer as well as patients with NCRNPD >24 weeks for patients with non-measurable disease

Progression-free survival (PFS) for the three different populations: Cohort A, Cohort B1, Cohort B2
	
PFS based on radiologic assessment by investigator using RECIST 1.1 criteria (e.g. median PFS, PFS rate at 12 and 18 months)

Overall survival (OS) for the three different populations, defined as the time from date of start of treatment to date of death due to any cause.
	
Overall survival (OS) (e.g. OS rate at 12 and 24 months)

Overall response rate (ORR) for the three different populations, defined as complete response or partial response as defined by RECIST 1.1
	
Overall Response Rate (ORR) after 24 weeks

To evaluate the safety and tolerability of ribociclib in combination with letrozole (and goserelin in premenopausal patients)
	
Frequency/severity of AEs AEs of special interest: Frequency, severity, frequency per patient, time to Event, duration of Event and recurrence

To evaluate patient reported outcomes for health related quality of life
	
Laboratory values Time to 10% deterioration in the global health status/QOL scale score of the EORTC QLQ-C30

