5.1 Definition of efficacy variables

Progression:

1. ds.eotdreasn = 4 (Main reason for ribociclib discontinuation = progressive disease)
2. ds.eotprdi1n = 1 (Radiologic progression according to RECIST 1.1) OR
3. ds.eotprdi3n = 1 (Clinically symptomatic progress) OR
4. zr.recoveran = 4 (Overall lesion response = Progressive Disease) OR
5. zr.recnewln=1 (New Lesion)

Progression date:

1. ds.eotcprdt (date of clinically symptomatic progress) OR
2. Date of Evaluation where zr.recoveran = 4 or zr.recnewln = 1

Response:

3. zr.recoveran (Overall lesion response)

Assessment Date:

4. zr.tlesdt (Date of image or examination, Target Lesion Assessment)
5. zr.ntlesdt (Date of image or examination, Non-Target Lesion Assessment)
6. zr.nlesdt (Date of image or examination at which new lesion appeared)

Date of Death:

7. sc.deathdt

Date of last contact:

8. sc.eoslcdt

Start of treatment = first administration of Ribociclib or Letrozole:

9. min(min(zq.ribostdt), min(zq.letrstdt))

5.1.1 Clinical Benefit Rate (CBR) until week 24

Best overall response in (CR, PR, SD, NCRNPD):

1. zr.recoveran = 1; at least two determinations of CR at least 4 weeks apart before progression OR
2. zr.recoveran = 2; at least two determinations of PR or better at least 4 weeks apart before progression (and not qualifying for a CR)
3. zr.recoveran = 3; two determinations of SD at least 12 weeks apart (and not qualifying for PR or PD)

4. zr.recoveran = 5

Tumor evaluations are scheduled for baseline, Cycle 4 and cycle 7 etc. (every 12 weeks). Thus, to assess the CBR at week 24 the first two post-baseline evaluations have to be considered. Additionally it has to be checked that no progression occurred during the following 4 weeks. Deviations against the time schedule is investigated and assessed during the data review meeting.

5.1.2 Overall response rate (ORR) by week 24

Similar to 5.1.1, but the best overall response must be in in (CR, PR)

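### The primary CBR derivation in SAP 5.1.1 does not implement the stated 24-week endpoint: SD that improves matches no rule, and NCRNPD needs no duration.

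*SAP*

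**What the plan says.** Protocol Table 3-1 gives the primary endpoint as the percentage of patients with "CR, PR or SD lasting 24 weeks or longer as well as patients with NCRNPD >24 for patients with non-measurable disease". SAP 1.2 says nearly the same: "CR, PR or SD until week 24 or longer as well as patients with NCRNPD >24 weeks for patients with non-measurable disease".

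The derivation is in SAP 5.1.1. It lists four ways to qualify:

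1. Two CR determinations at least 4 weeks apart.
2. Two determinations of PR or better at least 4 weeks apart.
3. For SD, "two determinations of SD at least 12 weeks apart (and not qualifying for PR or PD".
4. "zr.recoveran = 5", with nothing further.

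It adds that "to assess the CBR at week 24 the first two post-baseline evaluations have to be considered", these being the Cycle 4 and Cycle 7 scans. It also has a progression check ("Additionally it has to be checked that no progression occurred during the following 4 weeks") and a review step ("Deviations against the time schedule is investigated and assessed during the data review meeting").

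Protocol 10.4.1 carries the same SD rule: "To be assigned a stable disease, two determinations of SD at least 12 weeks apart (and not qualifying for PR or PD) are required". SAP 2.5.1 repeats it, except that the exclusion there names PR or CR instead of PR or PD, and it limits best overall response to assessments up to week 24.

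Two parts of Protocol Appendix 14.2 bear on this. Its Section 3.1 defines SD with the qualifier *or better*. Its Section 3.2.8 treats non-CR/non-PD as equivalent to SD when endpoints are determined.

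**The concern.** The trial tests no hypothesis, so the CBR estimate is its main result. Its meaning depends on the derivation matching the stated endpoint.

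Item 3 recognises only patients who are SD at both scans. A patient who is stable at week 12 and responding at week 24 has done at least as well, yet no item covers that course. Item 4 errs the other way, because it drops the duration that Table 3-1 and SAP 1.2 both require for NCRNPD. Some patients with documented disease control at week 24 would count as failures, and some with no week-24 evidence would count as benefit. Which error applies depends on whether the patient's disease is measurable.

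**Working it through.** **The plan's own precision figure.** Inputs from SAP Section 3: CBR 79%, n = 500, stated width 7.2 points. Wald width = 2 × 1.96 × √(0.79 × 0.21 / 500) = 7.14 points, which agrees within 0.1. The planned Clopper-Pearson method gives 7.33. At a CBR of 75% the two widths would be 7.59 and 7.77. Precision is not the issue.

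**Item 3, measurable disease.** Take the week-12 and week-24 scans, both evaluable, with no PD and no unscheduled scans. Three states at two scans give 9 sequences. Appendix 14.2, Section 3.1, does not allow CR to be followed by PR or SD, which leaves 7.

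| Week 12 | Week 24 | Item met |
|---|---|---|
| CR | CR | 1 |
| PR | CR | 2 |
| PR | PR | 2 |
| SD | SD | 3 |
| SD | PR | none |
| SD | CR | none |
| PR | SD | none |

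Three of the 7 sequences match nothing. This counts sequences, not patients. A PR first seen at week 24 can be confirmed only by a scan at least 4 weeks later, which falls outside both the two-scan limit and the week-24 cut-off.

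PR-SD is not a contrived case. The worked example in Appendix 14.2, Section 3.1 (sum of diameters 200 mm at baseline, then 140, 150, 140, 160, 160) is scored PR-SD-PR-PR-PR. With only its first two scans, that patient meets no item.

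**Item 4.** SAP 5.1 uses code 4 for PD, and items 1 to 3 use codes 1 to 3 for CR, PR and SD. Code 5 is therefore inferred to be NCRNPD, the remaining category in the 5.1.1 list. Set beside SD:

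| Course | Non-measurable (NCRNPD) | Measurable (SD) |
|---|---|---|
| Stable at week 12, then UNK or no scan | benefit (item 4) | no benefit |
| Stable at week 12, CR at week 24 | benefit (item 4) | no benefit |

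The 4-week progression check might remove NCRNPD followed by PD, depending on when it starts. It cannot remove NCRNPD followed by UNK, and it cannot restore SD-PR.

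**Definition behind the 79%.** Protocol Table 1-4 requires more than 24 weeks for both SD and NCRNPD. The printed rates correspond to 22/28 = 78.6% (Clopper-Pearson 59.0 to 91.7; printed 59 to 92) and, in measurable disease, 19/24 = 79.2% (57.8 to 92.9; printed 58 to 93). So 22 − 19 = 3 of the 4 NCRNPD patients counted. Had the fourth counted on a bare code, the rate would have been 23/28 = 82.1%, or 3.6 points higher. This is an illustration from 28 patients, not a forecast.

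**Scan interval.** With 28-day cycles, Cycle 4 Day 1 is day 1 + 3 × 28 = 85 and Cycle 7 Day 1 is day 1 + 6 × 28 = 169, which is 84 days apart. Protocol 7.2.1 allows ±7 days per scan, so the interval is 84 + (b − a) with a and b from −7 to +7, a range of 70 to 98 days. Of the 15 × 15 = 225 offset pairs, 15 × 14 / 2 = 105 fall below 84 days. This is a count, not a predicted share. It matters only if 12 weeks is read as 84 calendar days.

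**Scale.** One point of CBR at n = 500 is 5 patients. The planned half-width at 79% is 1.96 × √(0.79 × 0.21 / 500) = 3.57 points, or 0.0357 × 500 ≈ 18 patients. A net misclassification of about 18 patients would move the estimate by one half-width.

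**The case against.** The strongest defence is that the missing words can be supplied from elsewhere. Protocol 10.4.1 refers to Appendix 14.2, whose SD rule does say *or better*. The SAP 2.5.1 exclusion of patients who qualify for PR or CR does any work on two scans only if SD includes better responses. For NCRNPD, the duration stands in the endpoint statement, and the appendix's equivalence with SD could carry the SD rule across.

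This shows what was probably meant, but it does not settle the rule. The appendix needs only one SD assessment more than 6 weeks after start, which conflicts with two determinations 12 weeks apart, so it cannot simply be imported. Item 4 as written remains a bare code.

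The plan also has safeguards. SAP 2.5.1 promises a review, before analysis, of how confirmation interacts with the visit schedule, and adds a CBR at end of treatment. Missing tumour evaluations can lead to exclusion from the per-protocol set. These are real, but they yield sensitivity or additional results and leave the primary rule unchanged.

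On the scan interval the defence largely succeeds. A reader might infer that compliant SD pairs 70 to 83 days apart will be failed. The documents do not show this: SAP 5.1.1 itself ties 12 weeks to the Cycle 4 and Cycle 7 scans, and a visit-based reading passes every in-window pair. What remains is an ambiguity. The SAP does not say which reading applies, and it is unclear whether an in-window scan is a schedule deviation for the data review meeting.

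**Conclusion.** The concern holds for items 3 and 4. As written, the primary derivation counts SD-PR, SD-CR and PR-SD as no benefit in measurable disease, and it counts a single NCRNPD as benefit without the required duration. The 12-week interval is an ambiguity only.

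Item 3 lowers the CBR and item 4 raises it. The net size and direction cannot be determined, because the documents give no share of patients who first respond at week 24, lose an unconfirmed PR, or have NCRNPD without a week-24 assessment. A reader might try to size the item 3 effect from Table 1-4, or read 3 of 7 sequences as a share of patients. Neither is supported: the table gives best response over the whole study without its timing, it covers first-line patients only and so says nothing about cohort B, and the sequences are not equally likely.

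The conclusion assumes that code 5 is NCRNPD and that there are no unscheduled scans.

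**What to change.** In SAP 5.1.1, with Protocol 10.4.1 and SAP 2.5.1 aligned:

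- Reword item 3 as SD or better at the week-12 and week-24 assessments, with no progression and not qualifying for confirmed CR or PR. An unconfirmed CR or PR counts as at least SD.
- Apply the same rule to NCRNPD in item 4.
- State that scans within the ±7 day window count as the week-12 and week-24 assessments. This removes the interval ambiguity.
- Replace the exclusion of PR or PD with PR or CR, and state when the 4-week progression check starts and ends.
- Keep patients without a week-24 assessment in the FAS denominator as non-benefit. SAP 2.5.3 says this about unknown responses only for the ORR.
- If wanted, use a later adequate scan in place of a missing or unknown week-24 scan as a sensitivity analysis, not in the primary rule.
- Date and justify the change, and report the CBR under the present wording alongside. SAP 2.14 describes interim efficacy analyses as already run, and SAP 1.1 describes even the primary analysis in the past tense.

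No new data are needed. The cost is SAP rewording, reprogramming of one derivation, and a protocol amendment with the approvals in Protocol 12.1. The reported CBR may move in either direction. Because two assessments are still required, a patient with UNK at week 12 and NCRNPD at week 24, who now counts as benefit, would no longer do so; the SAP should say that this is intended.

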5.1.3 Progression-free survival

Start date = Start of treatment (first administration of Ribociclib or Letrozole)

End date = First date of progress or date of death or (if no event) date of last tumor assessment

5.1.4 Overall survival (OS)

Start date = Start of treatment (first administration of Ribociclib or Letrozole)

End date = Date of death or (if no event) date of last contact

5.2 Definition of safety variables

5.2.1 Duration of study treatment exposure

For ribociclib and letrozole the duration of exposure (days) = date of last administration of ribociclib resp. letrozole – date of first administration of ribociclib resp. letrozole + 1 day. The first administration of the study treatments ribociclib and letrozole are taken from the respective Dosage Administration Record, i.e. the date of first dose > 0 at/after C1/D1. The date of last administration of the study treatments ribociclib and letrozole are taken from the Treatment Completion CRF. In case of ongoing treatment, resulting in missing end days on Treatment Completion CRF, the end date is substituted hierarchy by:

- End date of last administration with dose >0 of ribociclib resp. letrozole on the Dosage Administration record before End-of-Treatment-visit
- If the end date of the last administration with dose >0 of ribociclib resp. letrozole on the Dosage Administration is missing (normally because “ongoing” is ticked) the date of the last visit during the on-treatment period (C1/D1 to End-of-treatment) is used to substitute the end date.

For goselerin the duration of exposure (days) = date of last administration of goselerin – date of first administration of goselerin + 1 day. The first administration of the study treatment goselerin is taken from the respective Dosage Administration Record, i.e. the first dose > 0 at/after C1/D1. The end of the third component goselerin is not asked at the Treatment Completion CRF and must be derived from the Dosage Administration record therefore. Goselerin may be continued in combination with a follow-up therapy and may be documented on the Dosage Administration Record, although it is no longer a study treatment. For this reason

the date of last goselerin administration is the last dose > 0 administered until the End-of-treatment visit.

The exposure to study treatment is displayed for each of the third components separately, and in combination. For combination, called “exposure to any of the study treatments”, the first start date and the last end date of the study treatments is used for calculation.

The duration of exposure includes the periods of temporary interruption (of any component of the study treatment for any reason).

5.2.2 Cumulative dose

Cumulative dose (mg) = total dose given during study treatment exposure

For patients who do not receive any drug the cumulative dose is set to zero.

5.2.3 Dose intensity (DI)

Dose intensity (mg/day) = cumulative dose (mg) / duration of exposure of study treatment (days)

For patients who do not receive any drug the dose intensity is set to zero.

5.2.4 Planned dose intensity (PDI)

Planned dose intensity (mg/day) = total daily dose prescribed

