6.1.1 Dosing regimen

Table 6-1 Dose and treatment schedule

Study treatments	Pharmaceutical form and route of administration	Dose	Frequency and/or Regimen
Ribociclib	Tablet for oral use	600 mg (3x200mg)	Once daily - Days 1-21 of each 28 day cycle
Letrozole	Tablet for oral use	2.5 mg	Once daily
Goserelin (for premenopausal patients)	Subcutaneous implant	3.6mg	Day 1 of each cycle

Ribociclib will be given orally once a day on days 1-21 of each 28 day cycle. Days 22-28 will be a “rest” from ribociclib. Letrozole will be given every day. Goserelin will be injected monthly for pre- or perimenopausal patients only.

Ribociclib, letrozole and goserelin will be administered as a flat-fixed dose, and not by body weight or body surface area.

The investigator or responsible site personnel should instruct the patient to take the study drugs as per protocol (promote compliance). Drug accountability must be performed on a regular basis. Patients will be instructed to return unused study drugs to the site at the end of each cycle. The site personnel will ensure that the appropriate dose of each study drug is provided at each visit.

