2.4 Treatments (study treatment, rescue medication, concomitant therapies, compliance)

2.4.1 Study treatment / compliance

Duration (days) of study treatment exposure for patients who took at least one dose of any of the components of the study treatment was calculated as the difference between the last and first day of drug application +1 day. For details see 5.2.1.

The duration includes the periods of temporary interruptions for any reason. Additionally, duration of drug exposure was summarized using descriptive statistics separately for ribociclib, letrozole and goserelin, respectively.

The cumulative dose, dose intensity (DI) and relative dose intensity (RDI) were summarized by cohort. Cumulative dose is defined as the total dose given during the study treatment exposure. For patients who did not receive the respective drug the cumulative dose was set to zero (in case of goselerin for pre- and perimenopausal patients only). The dose intensity (DI) for patients with non-zero duration of exposure is defined as cumulative dose / duration of exposure. For patients who did not receive any drug, the DI was set to zero. Planned dose intensity (PDI) is the assigned dose in mg/day prescribed by the investigator to be given to patients. Relative dose intensity (RDI) is defined as DI divided by PDI. The DI and RDI were summarized separately for each of the study treatment components, but using the duration of the whole study treatment exposure, not the duration of each of the components. In addition, for combinations, the RDI was calculated as mean RDI of each of the study treatment components on a per-patient basis.

Ribociclib interruptions (defined as null doses for any reason except “as per protocol”) were displayed by the number of affected patients, the total duration and frequencies of study drug interruptions. The total duration was calculated by end date – start date of interruption (for any reason except “as per-protocol”) + 1 day. All interruptions of a patient are summed up to the total duration (for any reason except “as per protocol”)

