Frequencies of the number of patients with ribociclib dose reduction (defined as dose > 0 mg but lower than the previous dose) as well as the number of dose reductions by reason were given. Additionally, dose reductions and dose interruptions were tabulated in combined fashion. In the combined summary, the dose interruptions were considered as dose reductions to 0 mg and therefore all reductions/interruptions were labeled as reductions and tabulated in one table.

These analyses were performed for the Safety Set (SAF).

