5.2.5 Relative dose intensity (RDI)

Relative dose intensity (mg/day) = dose intensity (mg/day) / planned dose intensity (mg/day)

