5.2.6 Mean relative dose intensity (mean RDI)

Mean relative dose intensity (mg/day) = mean of the relative dose intensity per patient by study treatment component

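### Ribociclib planned dose intensity ignores the 21-of-28-day schedule, so full adherence gives a relative dose intensity of 75% over whole cycles instead of 100%

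*SAP*

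**What the plan says.** Protocol Table 6-1 schedules ribociclib 600 mg "Once daily - Days 1-21 of each 28 day cycle", letrozole 2.5 mg once daily without a break, and goserelin 3.6 mg as one implant on day 1 of each cycle.

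SAP 5.2.3 defines dose intensity (DI) as cumulative dose over the duration of study treatment exposure. SAP 2.4.1 says that DI and RDI are computed for each component "using the duration of the whole study treatment exposure, not the duration of each of the components". SAP 5.2.1 runs the combined exposure from the first start to the last end of any component and leaves interruptions in.

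Planned dose intensity (PDI) is defined twice. SAP 2.4.1: "Planned dose intensity (PDI) is the assigned dose in mg/day prescribed by the investigator to be given to patients". SAP 5.2.4: "Planned dose intensity (mg/day) = total daily dose prescribed". RDI is DI divided by PDI (SAP 5.2.5). SAP 5.2.6 adds "Mean relative dose intensity (mg/day) = mean of the relative dose intensity per patient by study treatment component".

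**The concern.** The DI denominator counts every calendar day, because daily letrozole carries the exposure window through the ribociclib rest weeks. The PDI is a dose per dosing day. Dividing one by the other turns the scheduled week off into apparent under-dosing.

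Safety and tolerability is a secondary objective, and DI and RDI are to be summarised by cohort. On these definitions, a patient who took every tablet cannot be told apart by RDI from one who lost a quarter of the dose to reductions or interruptions. Nor could the results be set against the median ribociclib RDI above 98% that Protocol 1.2.6 reports for the earlier study on the same 600 mg, 21-of-28-day schedule. Over whole cycles at 600 mg, this formula cannot exceed 75%.

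Three related points are open or mislabelled:

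- Goserelin has no daily dose, so its PDI in mg/day is undefined.
- The SAP does not say whether PDI is the starting or the current prescribed dose.
- RDI and mean RDI are ratios but carry the unit mg/day in SAP 5.2.5 and 5.2.6.

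**Working it through.** The SAP states no RDI value to reproduce, so the check applies its formulas to a fully adherent patient.

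**Inputs.** Ribociclib 600 mg on 21 of 28 days, letrozole 2.5 mg on all 28 days, goserelin 3.6 mg once per 28 days (Protocol Table 6-1). Duration = last day − first day + 1 over all components (SAP 2.4.1, 5.2.1). Ribociclib PDI = 600 mg/day (SAP 5.2.4).

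**Whole cycles (n cycles).**
- DI = 600 × 21n / 28n = 450 mg/day
- RDI = 450/600 = 75%, for any n
- With PDI = 600 × 21/28 = 450 mg/day: RDI = 450/450 = 100%

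**All treatment stops on day 21 of the last cycle (k cycles).** There are 21k dosing days in 28(k − 1) + 21 calendar days.

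| k | Dosing days / calendar days | RDI as written | RDI with PDI 450 mg/day |
|---|---|---|---|
| 1 | 21/21 | 100% | 133.3% |
| 6 | 126/161 | 78.3% | 104.3% |
| 12 | 252/329 | 76.6% | 102.1% |
| 20 | 420/553 | 75.9% | 101.3% |

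The last column is the third column divided by 0.75. If PDI is instead 600 × (scheduled dosing days in the window) / (days in the window), RDI is 100% in every row.

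**Mean RDI at full adherence, whole cycles.**
- Ribociclib and letrozole: (75% + 100%)/2 = 87.5%
- With goserelin, PDI taken as 3.6/28 mg/day (assumption): (75% + 100% + 100%)/3 = 91.7%
- With goserelin, PDI taken as 3.6 mg/day (assumption): goserelin RDI = 1/28 = 3.6%, and the mean is (75% + 100% + 3.6%)/3 = 59.5%

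**Starting or current dose.** Take an adherent patient with three cycles at 600 mg and three at 400 mg. DI = (3 × 21 × 600 + 3 × 21 × 400)/168 = 63,000/168 = 375 mg/day. The average prescribed dose on dosing days is 500 mg.

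| PDI basis | No schedule factor | With 21/28 factor |
|---|---|---|
| Starting dose, 600 mg | 375/600 = 62.5% | 375/450 = 83.3% |
| Current dose, average 500 mg | 375/500 = 75% | 375/375 = 100% |

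**The case against.** The strongest reply is that PDI is underspecified rather than wrong. Neither definition says how a prescribed dose that varies over time is aggregated. Protocol 6.5.3.1 requires the planned dose to be recorded with start and end dates. SAP 2.4.1 refers to null doses given as per protocol, which suggests that rest weeks are entered as 0 mg. A programmer could average the prescribed dose over all calendar days, get 450 mg/day, and report 100%. In the dose-reduction example the same averaging gives 375 mg/day and again 100%. The RAP modules that SAP 2.1 cites are not among the documents, so the tables actually produced cannot be seen.

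The last part stands: the finding concerns the SAP's wording, and what was programmed is unknown. The averaging rule itself is stated nowhere. The as-per-protocol exemption applies only to counting interruptions, and both PDI definitions read as a daily dose. If calendar averaging was used, the SAP misdescribes its own output and still needs correcting.

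Several smaller objections are fair. RDI is descriptive, Protocol 10.3 does not ask for it, and interruptions and reductions are tabulated separately. Reading the goserelin implant as a daily dose is implausible; it shows only that the definition does not cover that drug. The mg/day label is clerical. The 80–120% intake window in deviation S_03 is not tied to RDI, and S_03 is absent from the per-protocol list in SAP Table 2, so no effect on the Per-Protocol Set is claimed.

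**Conclusion.** The concern holds. Applied as written, the SAP gives a fully adherent patient a ribociclib RDI of exactly 75% over whole cycles. If all treatment ends on day 21 of the last cycle, the value is 78.3% at 6 cycles and 75.9% at 20, and it reaches 100% only for a single cycle. The per-patient mean RDI inherits the error.

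This rests on the 600 mg dose, letrozole running through the rest weeks, and PDI taken as the literal daily dose. The goserelin figures rest on assumed readings. The damage is limited to descriptive exposure tables in the Safety Set. It should be corrected because those tables would misstate adherence and could not be compared with the earlier study's figure.

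**What to change.** Amend SAP 2.4.1 and 5.2.4–5.2.6 as follows.

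1. Define PDI for each component as the total dose scheduled on dosing days within the patient's own exposure window, divided by the calendar days in that window. A simpler version uses scheduled mg per 28-day cycle divided by 28 (ribociclib daily dose × 21/28, letrozole daily dose, one goserelin implant/28). Its drawback is that RDI exceeds 100% when exposure ends on day 21 of the last cycle. The window-based form avoids this.
2. State whether the planned dose is the starting or the current prescribed dose.
3. Report RDI and mean RDI as percentages.
4. As a secondary wording point, SAP 2.4.1 counts a "dose reduction (defined as dose > 0 mg but lower than the previous dose" without saying whether a 0 mg record is the previous dose. If it is, a 600–0–400 mg sequence is missed in the stand-alone reduction table, although the combined table would still show the patient. State that reductions are judged against the last non-zero dose.

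If exposure tables already exist, check which PDI was programmed before they are used. The cost is SAP text and reprogramming of the exposure tables. No new data are needed, and no dosing rule changes.
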